*Interactions between AEE and site:* Multiplicative interaction terms will be included in regression models to assess how much site modifies the association between AEE and the risk factor. We are fully aware of the lack of statistical power to test this type of hypotheses and thus results will be exploratory in nature. Thus, one might anticipate that anthropometric and AEE measures are stronger in low risk population samples than in the US. In addition, we will test whether the slope of the exposure-outcome relationships are influenced by the mean BMI of the population using multilevel regression models.

Questionnaire data on AEE will be summarized using methods previously developed [188]. Mean activity levels and prevalence of inactivity will be assessed in relation to objective measures of EE and the relevant outcome variables. As a sub-analysis we will describe types of activities reported to assess overall population patterns.

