#### D.7.1.3 Comparison of Mean AEE Levels Among Sites

The 2 sample t-test will be used to compare means of the primary continuous variables, e.g., BMI, PA, weight, and height. Relevant co-variates will be identified from the within-site analyses and added using multivariable models [186, 190]. We recognize that some modifying factors within sites may not have the same significance across sites, and we will be very careful how variables are chosen for these analyses. Finally, we will test whether the regression slopes of the PA-BMI relationship varies significantly among any pair of sites (i.e., test for interaction).

The association between mean levels of AEE and mean levels of obesity/relative weight will be assessed using regression analysis, following a meta-regression type of approach. That is, mean AEE values will be regressed on mean obesity/relative weight values, weighting by the inverse of the squared standard error of the mean AEE values [191]. This is a widely-used approach in meta-analysis [192]. It is recognized that EI is an important potential confounder of the associations at the individual level. We will estimate the median (and other quantiles of the distribution) usual intake of nutrients (e.g. fat, percent fat) using methods developed by the ISU research group [179, 193] and include them in the meta-regression models.

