## D.7.2 Power Analysis

A statistical justification for the selected sample size is provided for each aim of the study according to the suggested analytical plan. Sample size estimation for each of these hypotheses will be obtained, and the maximum number required to test them with sufficient power (80% or higher) will be selected.

- 1) PA is negatively related to percent body fat and CV risk factors in the study populations at baseline.

It has been previously estimated (cf. Preliminary Studies) that the correlation between PA, measured with DLW, and body composition is between -0.6 and -0.5. A correlation of -0.33 or smaller (larger in absolute value) will be detectable with 83% power and maximum probability of type I error alpha = 5% using a one-sided Fisher's Z test and 75 subjects per site [194].

- 2) PA is negatively related to change in body fat composition.

- a) *Physical Activity Measured by Accelerometer:*

PA, measured by the accelerometer, is associated with changes in body composition. For design purposes we will use the approach described above in the analysis section (see D.7.1.2. method 3). That is, two AEE groups will be formed by using the median AEE as the cut point. A method developed by Frison and Pocock [195] will be applied to compare mean changes between groups in a longitudinal analysis, adjusting for baseline values. In this method the following assumptions are made: the correlation between any 2 weight determinations is ~ 0.60 and the minimum acceptable difference between the means is 0.25 standard deviations (i.e., effect size equals 0.25) [186]. There will be one baseline measure of weight and two follow-up measurements. An analysis of covariance approach will be used to adjust for baseline values. Thus, to detect the pre-specified minimum difference with 90% statistical power we will need to accrue 460 subjects per AEE group (230 in the Low and 230 in the High group). We will accrue a total of 500 individuals per site in anticipation of a conservative total attrition rate of ~ 20%.

- b) *Physical Activity Measured by Doubly Labeled Water:*

The correlation between AEE and change in body composition is anticipated to be weaker (i.e., smaller in absolute value) than that observed between AEE and body composition at baseline. Data from previous studies (cf. Section C: Preliminary Studies) suggest that the association between AEE and body composition remains constant across studies.

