Although the study is not powered to test for differences in the association across sites (i.e., effect modification), we will undertake this task to ensure that large differences among the correlation coefficients do not exist. In addition, sites in which the correlation coefficient is deemed to be similar will be combined, and then comparisons of the correlations will be performed. For the sake of illustration, assume that 2 sites ( $n = 150$  individuals) are compared to other 2 sites ( $n = 150$  individuals). Thus, a two-sample, one-sided test of the correlations, assuming -0.4 versus -0.65, will yield over 91% power, whereas the power will be over 80% for comparison of -0.45 and -0.65, and between -0.35 and -0.6 the power is greater than 85%. Combining the data samples from all 5 sites and assuming constant

association will demonstrate a correlation between AEE and change in body composition of -0.15 or smaller (larger in absolute value) with over 83% power.

3) Mean levels of AEE are negatively related to mean levels of obesity/relative weight among the populations.

As previously demonstrated, sample sizes within sites will allow us to rule out correlations larger than 0.33 (absolute value), even when AEE is determined by DLW. Furthermore, we have estimated (cf. Preliminary Studies) that the within-site correlation between AEE and body composition of individual data could be as large as 0.6. We anticipate that the correlation between mean AEE levels and mean body composition will exceed 0.85. This estimate is justified in the following manner. A Fisher's Z-transformation 5%-significance test will have over 55% power to detect this correlation with 5 values corresponding to the 5 sites of the study. However, after dividing our samples by gender there will be 10 observations (2 X 5 countries), resulting in over 95% statistical power. Assuming an effective sample size of 7, to account for within-country correlations, the statistical power is 80%. Note that additional power will be gained when weighted linear regression methods are applied to estimate the correlation (slope) between AEE and body composition using meta-regression. Given the strong a prior hypothesis we can also compare mean AEE in the groups with the highest and lowest rates of obesity to test the ecological association.

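### Item 2b combines sites with similar correlations and then compares the correlations, with no groups or criterion fixed in advance; if the study's own correlations form the groups, the nominal 5% error does not hold

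*Combined protocol and SAP*

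**What the plan says.** Section D.7.2, item 2b, concerns activity energy expenditure (AEE) measured by doubly labelled water, with 75 participants per site. It concedes that the study is not powered for differences between sites, but adds that "we will undertake this task to ensure that large differences among the correlation coefficients do not exist". The next step is that "sites in which the correlation coefficient is deemed to be similar will be combined, and then comparisons of the correlations will be performed".

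The layout is an example: "For the sake of illustration, assume that 2 sites" (150 people) are set against two others (150 people). For this, "a two-sample, one-sided test of the correlations, assuming -0.4 versus -0.65, will yield over 91% power". The plan also gives over 80% for -0.45 v -0.65 and more than 85% for -0.35 v -0.6. Item 2b states no significance level; item 1 of the same section uses 5% one-sided. The item ends with a power figure for all five sites pooled, introduced by "Combining the data samples from all 5 sites and assuming constant" association.

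Related text elsewhere:
- D.7.1.1.1 plans Fisher's Z and approximate permutation tests for comparing correlations.
- D.7.1.1.2 says "Multiplicative interaction terms will be included in regression models to assess how much site modifies the association between AEE and the risk factor", and calls those results exploratory.
- D.7.1.2 makes a multilevel model the final analysis of weight change and allows site-specific factors in it.
- D.7.1.3 says "we will test whether the regression slopes of the PA-BMI relationship varies significantly among any pair of sites".

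**The concern.** A two-sample test of correlations has its nominal error rate when the two groups are chosen without regard to the correlations being tested. If sites are sorted by their observed correlations and the resulting groups are then compared, the contrast is large by construction, even when all sites share one true value.

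Two things are at stake. Chance differences between groups of sites could be reported as effect modification. Conversely, a strict notion of similarity could hide real differences in a check whose stated purpose is to rule out large ones.

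**Working it through.** **Inputs.** From the plan: five sites, 75 per site (D.3.2, D.7.2); the three pairs of correlations and the 150 v 150 layout (D.7.2, item 2b); up to 20% attrition by 24 months (D.1.1). Assumed: the 5% level of item 1 carries over to item 2b.

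**Step 1: the plan's own powers.** Power = Φ(|atanh r₁ − atanh r₂| / √(1/(n₁−3) + 1/(n₂−3)) − 1.645). At 150 v 150 the standard error is √(2/147) = 0.1166. At 120 v 120 (20% lost) it is √(2/117) = 0.1307.

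| Contrast | Difference in z | Plan states | 150 v 150 | 120 v 120 |
|---|---|---|---|---|
| -0.4 v -0.65 | 0.3516 | over 91% | 91.5% | 85.2% |
| -0.45 v -0.65 | 0.2906 | over 80% | 80.1% | 71.8% |
| -0.35 v -0.6 | 0.3277 | over 85% | 87.8% | 80.6% |

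For the first row: 0.3516/0.1166 = 3.015; 3.015 − 1.645 = 1.370; Φ(1.370) = 0.915. All three stated figures reproduce at 150 v 150. At 120 v 120 each falls below its stated bound. Tested two-sided at 150 v 150, the powers are 85.4%, 70.2% and 80.2%.

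**Step 2: error rate when the data form the groups.** Give all five sites one true correlation. Each site's Fisher z then has variance 1/72. Sort the sites, form two groups of a and b sites, and compare the group mean z values using standard error √(1/(72a) + 1/(72b)). The direction of the test follows the data. Share of simulated studies rejecting:

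| Grouping | One-sided 5% critical value (1.645) | Two-sided 5% critical value (1.96) |
|---|---|---|
| Lowest v other four | 24% | 12% |
| Two lowest v other three | 38% | 21% |
| Two lowest v two highest | 48% | 29% |
| 2 v 2, fixed in advance | 5.0% | 5.1% |

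Simulation of raw bivariate-normal data gives the same rates at true correlations of -0.5 and -0.15, and almost the same with 60 per site. If the one-sided direction were fixed independently of the data, the rates in the first column would roughly halve (48% to about 24%).

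**Step 3: a test that needs no grouping.** Q = 72·Σ(z − z̄)² against chi-square on 4 df rejects in 5.0% of null studies. If a group comparison is made only after a significant Q, the overall error stays at 5.0%.

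For power, put two sites at each illustrated value and the fifth midway on the z scale. The noncentrality is then (m − 3) × (difference in z)², with m the number per site. For the first contrast and m = 75 this is 72 × 0.3516² = 8.90. Power for the three contrasts is 66%, 48% and 59% with 75 per site, and 54%, 38% and 48% with 60 per site.

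**The case against.** The strongest reply is that the defect is conditional. The plan never says that the groups come from its own correlations, and any error rate depends on a splitting rule that the plan does not contain. That stands: the figures in step 2 show what would happen under stated rules. A reader might infer that the plan has a false-positive rate near 50%. The documents do not support that, because a restrictive similarity rule would give lower rates, as would a two-sided critical value or a direction set beforehand. What survives is that no rule is given and that, with the sites always split, every rule examined exceeds 5%.

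A second reply is that the plan already has safeguards. The permutation tests in D.7.1.1.1 would help only if the grouping step were repeated within each permutation, which is not stated. The exploratory label in D.7.1.1.2 belongs to risk-factor interactions. The test in D.7.1.3 concerns the slope on BMI, for any pair of sites. The multilevel model in D.7.1.2 allows site factors but specifies no test of homogeneity. None of these governs item 2b.

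A third is that the outcome is unclear. Item 2b opens with change ("The correlation between AEE and change in body composition is anticipated to be weaker"), but its illustrated values, -0.35 to -0.65, straddle the range of -0.6 to -0.5 given for body composition in item 1. On a baseline reading, 75 per site is right and the quoted powers stand for pre-fixed groups. The attrition-adjusted figures apply only if the outcome is 24-month change.

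Finally, this is a side-check, and the plan says that it is not powered. That stands and sets the priority. It would also be too strong to say that pooling all five sites depends on passing the check: the plan states constant association as an assumption of a power figure, not as a decision rule.

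**Conclusion.** The concern holds in a limited form. Item 2b describes a combine-then-compare step with no groups and no criterion. On the natural reading, the nominal 5% error does not hold: about 24% to 48% of null studies reject one-sided in the observed direction, and about 12% to 29% with a two-sided critical value. These figures assume five sites always split by their observed correlations and one common true correlation.

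A reader might also infer that the quoted powers are miscalculated. They are not: they are right for groups and direction fixed in advance with 150 v 150 analysed. If the outcome is 24-month change and 20% are lost, they become about 85%, 72% and 81%, all short of the stated bounds.

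Nothing here touches the sample size, which does not rest on this comparison. Low priority.

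**What to change.** Replace the combine-then-compare step with one global two-sided 4-df test of homogeneity across the five sites. This can be an AEE-by-site interaction for the item 2b outcome, or a Fisher-z test if correlations are kept. Report each site's estimate with its 95% confidence interval. Compare groups of sites only if the groups are fixed before the data are seen; otherwise compare them two-sided after a significant global test, or label the comparison descriptive. If permutation tests are used on data-derived groups, repeat the grouping within each permutation.

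Add two statements: that the quoted powers apply only to pre-fixed groups tested one-sided with 75 per site analysed, and that a non-significant global test does not show that large differences are absent. Say whether item 2b concerns baseline or change.

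The change is to SAP wording only. Its price is power: about 66%, 48% and 59% for the three illustrated contrasts with 75 per site, and 54%, 38% and 48% with 60, if the fifth site lies midway. A correctly pre-fixed contrast would have more.

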#### **D.7.1.1 Weight and Body Composition are Related to AEE at Baseline**

##### **D.7.1.1.1 AEE, Weight and Body Composition**

Two measures of AEE will be available. At baseline, we will have 500 participants/site with data from the accelerometer, inclusive of those who have both DLW and accelerometer (total N, all sites = 2500; 6 days

of monitoring). We will have data generated by DLW for 75 participants/site (total N, all sites = 375). The structure of the analysis will be similar with both exposure measures.

We anticipate that data for all the primary outcomes will not conform entirely to a normal Gaussian distribution. Using BMI, PAL and AEE data collected in previous studies in Maywood (n = 567) and Nigeria (n = 735), we examined the probability distributions. A formal test statistic was performed that combines kurtosis and skewness [180] as implemented in STATA with p-values less than 0.001, suggesting deviations from normality. Kernel density estimates of the BMI, AEE, and PAL distributions are depicted in Figure 7. After applying the ladder of power approach suggested by Tukey [181], we found that BMI, AEE and PAL for both sites appear to deviate from normality. Although no transformation is preferred after application of the ladder of powers method, two potential transformations are suggested by this approach, namely  $\log X$  and  $X^{-1}$ . Tukey's approach followed by formal testing will be carried out once data on all subjects in the study has been collected and a decision about data transformations has been made. Despite the lack of normality exhibited and corroborated by the statistical tests performed, a visual exploration of Figure 7 suggests only slight deviations from normality, mostly due to well-known skewness of these distributions. Thus, we anticipate the statistical methods that make use of normally distributed data will be appropriate to analyze these data. Of course, the degree of appropriateness of these methods will depend on their robustness to deviations from normality. If it is necessary, appropriate transformations will be carried out before statistical tests are performed.

**Figure 7.** Distribution estimates of main analysis variables BMI, AEE, and PAL in two sites: Maywood (US) and Nigeria.

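### The illustrative power figures for comparing correlations between site groups are one-sided, though the check has no direction; two-sided they are about 85%, 70% and 80%.

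*Combined protocol and SAP*

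**What the plan says.** Item 2b of D.7.2 concerns AEE measured by doubly labeled water. It first concedes that the study lacks the power to test whether the association differs across sites, then says that "we will undertake this task to ensure that large differences among the correlation coefficients do not exist". The method is that "sites in which the correlation coefficient is deemed to be similar will be combined, and then comparisons of the correlations will be performed". By way of illustration it sets two sites against two others, 150 participants in each group, and reports that "a two-sample, one-sided test of the correlations, assuming -0.4 versus -0.65, will yield over 91% power". For the other two pairs of correlations, "the power will be over 80% for comparison of -0.45 and -0.65, and between -0.35 and -0.6 the power is greater than 85"%. It gives no reason for the one-sided test and no significance level for this comparison.

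The 150 per group follows from D.7.1.1.1: "We will have data generated by DLW for 75 participants/site (total N, all sites = 375"). The nearest stated significance level is in item 1 of D.7.2: "maximum probability of type I error alpha = 5% using a one-sided Fisher's Z test and 75 subjects per site".

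The related analysis text is not directional. D.7.1.3 plans an interaction test of whether the PA–BMI slope differs between any two sites. D.7.1.1.1 plans two-sample and permutation comparisons of correlations and names no side.

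**The concern.** A check for heterogeneity asks whether associations differ, whichever group is stronger. A difference of either sign would undermine pooling, and the same paragraph goes on to assume a constant association when it combines all five sites. A one-sided test fits only if the order of the groups is set beforehand. Here the groups are to be formed from sites judged to have similar correlations, so the order cannot be known until the correlations have been seen.

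Two things would follow if the one-sided test were carried into the analysis. With the direction fixed arbitrarily, a difference the other way would almost never be found. With the direction taken from the data, a nominal 5% test would have a 10% type I error. Even if neither happens, the printed powers are more favourable than those of a test suited to the stated purpose.

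**Working it through.** **Inputs.** Correlations of -0.40 v -0.65, -0.45 v -0.65 and -0.35 v -0.60, with 150 per group (2 × 75), come from D.7.2 item 2b and D.7.1.1.1. Alpha of 5% is an assumption for this comparison, taken from item 1 of D.7.2.

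**Formula.** Two-sample Fisher's Z, using absolute values of the correlations:

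- d = atanh(r2) − atanh(r1)
- SE = √(1/147 + 1/147) = 0.1166
- z = d / SE
- one-sided power = Φ(z − 1.645)
- two-sided power = Φ(z − 1.960), the opposite tail being negligible

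**Results.**

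| Pair | d | z | Plan states | One-sided 5% | Two-sided 5% | Fall (points) |
|---|---|---|---|---|---|---|
| -0.40 v -0.65 | 0.7753 − 0.4236 = 0.3516 | 3.015 | over 91% | 91.5% | 85.4% | 6.1 |
| -0.45 v -0.65 | 0.7753 − 0.4847 = 0.2906 | 2.491 | over 80% | 80.1% | 70.2% | 9.9 |
| -0.35 v -0.60 | 0.6931 − 0.3654 = 0.3277 | 2.809 | over 85% | 87.8% | 80.2% | 7.6 |

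The one-sided column agrees with all three statements in the plan; the third is a loose lower bound. The two-sided column agrees with none of them, so the printed figures are one-sided, as labelled. A bivariate-normal simulation with 40,000 runs gives two-sided powers of 85.4%, 70.4% and 80.4%.

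**Difference in the other direction.** The power of the one-sided test is then Φ(−z − 1.645). This is largest for the middle pair, Φ(−4.136), or about 0.002%.

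**Effect of forming groups from the data.** Take five sites of 75 with the same true correlation, and pool the two strongest observed correlations against the two weakest. Simulated rejection rates are about 47% for the nominal one-sided 5% test and about 29% for the nominal two-sided 5% test. This is an extreme grouping rule that the plan does not specify. It shows that a two-sided test is not enough if the groups depend on the observed correlations.

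**The case against.** The strongest reply is that little rests on these numbers. Item 2b itself says that the study is not powered for cross-site differences and offers the figures only as illustration. D.7.1.1.2 likewise concedes low power for AEE-by-site interactions and calls those results exploratory. That stands, and it is why the point is minor.

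A reader might infer that the middle scenario, at 70%, misses the plan's own 80% criterion. The documents do not support this. The rule that "the maximum number required to test them with sufficient power (80% or higher) will be selected" concerns sample size for the listed hypotheses. Cross-site heterogeneity of the correlation is not one of them, and item 2b exempts it in terms.

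A reader might also infer that the plan commits itself to a one-sided heterogeneity analysis, with the missed differences or doubled error rate described above. It does not. The side appears only in the power illustration, while the analysis text in D.7.1.1.1 and D.7.1.3 names none. Those consequences are conditional.

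It can be said, too, that the plan does expect a direction. B.3 expects clearer risk relationships in developing countries, and D.7.1.1.2 suggests stronger ones in low-risk samples than in the US. Neither statement defines the two groups in item 2b, which are formed by similarity of correlation and not by risk level or stage of development. They do not justify a one-sided test there.

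Finally, a two-sided test does not repair grouping on observed correlations, and a non-significant result on either basis cannot establish that large differences are absent. Both remarks are right. The first has to be part of the fix.

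**Conclusion.** The point holds as a minor correction. The three powers are correctly computed for a one-sided 5% test, but that test does not match a check without direction on groups without a pre-specified order. On a two-sided basis they become 85.4%, 70.2% and 80.2%. This rests on alpha of 5%, which item 2b does not state, on 150 participants with data in each group, and on groups fixed independently of the observed correlations. No sample size is affected. The one-sided test of the AEE association in item 1 is a separate matter, because that hypothesis has a stated sign.

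**What to change.** In D.7.2 item 2b:

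- Make the comparison of correlations between site groups two-sided at 5%, in line with the non-directional interaction test in D.7.1.3.
- Restate the illustrative powers at 150 v 150 as about 85% (-0.40 v -0.65), 70% (-0.45 v -0.65) and 80% (-0.35 v -0.60).
- State that these powers and the 5% error rate hold only if the site groups are fixed without reference to the observed correlations.

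No remark about an 80% target is needed, since that criterion does not formally apply to this check. The cost is a change of wording and three illustrative figures that are about 6 to 10 points less favourable. Enrolment and data collection do not change.

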## B.9 Summary

Although the “obesity epidemic” has received enormous attention in recent years, the mechanisms through which the energy budget is being perturbed are still not well understood. In particular, the role of declining AEE as a causal mechanism in population-wide increases in relative weight deserves much greater attention. Despite widespread perception that variation in normal activity levels (as opposed to voluntary increases in high-intensity activity, as typical of trials) is correlated with change in weight, the data do not support this conclusion. Research in this vital area has been handicapped by lack of access to precise objective methods of measurement. A new generation of epidemiologic research will be required before we can base causal inferences or public health recommendations on something more than assumptions. As with other chronic CVD, international comparisons could be particularly informative.

The test of our study hypothesis will be “two-sided”. That is to say, the presence or absence of an association can be given a clear interpretation. Of course, given the body of evidence that increased AEE has health advantages, absence of an association would not be taken to suggest that AEE is of no value. Rather, the correct interpretation would be that declining AEE is unlikely to be the driving force behind the rise in obesity, nor will modest increases in AEE be adequate to reverse the trends.

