## D.8 Limitations

This study is based on the premise that objective measurement of EE will be required to fully understand the causes of the on-going secular trends in obesity. Given prior research on the role of specific sedentary activities, it is reasonable to test the hypothesis that AEE will vary across the social settings we have chosen to study. The value of our study will be in quantifying the overall magnitude of this difference and its within-site relationship. We recognize that it is possible that increases in energy intake—rather than expenditure—could be the determining, or even sole factor, in weight gain and diabetes risk; demonstrating the absence of a PA-obesity relationship will directly support this alternative hypothesis. We will capture data on EI from questionnaires as well, although we recognize its limitations.

On the other hand, the net positive energy balance required to cause gradual weight gain can be quite subtle (in the range of 20-40 kcal/d for adults). Given that this net excess is likely to be due to a combination of both decreased AEE and increased caloric intake, the contrast in population means for AEE could be hard to define. As in all such etiologic studies, therefore, we run the risk of a false negative due to low power. This result, however, would not be uninformative since it would be important to know that large mean shifts in AEE were not driving this epidemic. At the same time, a wide distribution of AEE levels can be anticipated among participants within each site, and we anticipate finding important relationships in the individual-level analyses. The entire success of the project, therefore, does not rest on the group comparisons.

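### D.7.2 restates power to detect a correlation of -0.33 as an ability to exclude correlations above 0.33 in absolute value, which the planned test does not give

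*Combined protocol and SAP*

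**What the plan says.** The baseline power statement in D.7.2 item 1 reads: "A correlation of -0.33 or smaller (larger in absolute value) will be detectable with 83% power", with "maximum probability of type I error alpha = 5"%, "using a one-sided Fisher's Z test and 75 subjects per site". The sample size agrees with D.7.1.1.1: "We will have data generated by DLW for 75 participants/site".

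D.7.2 item 3, on mean activity energy expenditure (AEE) and mean obesity across populations, opens by treating the within-site matter as already shown: "sample sizes within sites will allow us to rule out correlations larger than 0.33 (absolute value), even when AEE is determined by DLW". It gives no separate calculation for this, and no margin or exclusion rule appears elsewhere in the plan.

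Two other places show that a null result is meant to carry meaning. B.9 says that "the presence or absence of an association can be given a clear interpretation". D.8, discussing the possibility that intake is the determining factor in weight gain, says that "demonstrating the absence of a PA-obesity relationship will directly support this alternative hypothesis".

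D.7.1.1.1 plans Fisher-z and bootstrap confidence intervals for the correlations. It does not link them to any statement that an association is absent.

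**The concern.** Item 1 describes how often a test of r = 0 will reject when the true correlation is -0.33. Item 3 turns this into a statement about which correlations the data will exclude. These are different properties. A non-significant result says that zero is compatible with the data; it does not say that -0.33 is incompatible with them. The absolute-value wording adds a second problem, because a test that looks only for negative correlations cannot speak about positive ones.

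What is at stake is how a null DLW result at a site is read. If item 3 is taken at face value, non-significance at 75 subjects could be reported as excluding a correlation of moderate size while the interval still contains it. Because B.9 and D.8 give absence a substantive interpretation, the distinction matters here more than in a study that interprets only positive findings.

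**Working it through.** **Inputs.** n = 75 DLW subjects per site, one-sided alpha of 5%, r = -0.33 and stated power of 83% (D.7.2 item 1); Fisher-z intervals (D.7.1.1.1). On the Fisher scale, SE = 1/sqrt(75 - 3) = 1/sqrt(72) = 0.1179 and atanh(0.33) = 0.3428. The ratio is 0.3428/0.1179 = 2.909.

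**Step 1: the plan's own figure.** Power = Phi(sqrt(n - 3) x atanh(0.33) - z_crit).
- One-sided 5%, n = 75: Phi(2.909 - 1.645) = 89.7% (simulation: 90.1%).
- Two-sided 5%, n = 75: Phi(2.909 - 1.960) = 82.9%.
- One-sided 5%, n = 60 (75 less 20%): 82.7%.

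The stated 83% is therefore not what the stated one-sided test gives. It is conservative for those inputs and matches either a two-sided test or about 60 evaluable subjects. The main point does not depend on which was meant.

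**Step 2: what a non-significant result leaves open.** The one-sided critical value is tanh(1.645 x 0.1179) = 0.191. At r = -0.191, where z = -0.194, the 95% interval is tanh(-0.194 ± 1.960 x 0.1179), or -0.40 to +0.04. The one-sided 95% bound is -0.37. Both leave -0.33 in play. For a two-sided test the critical value is -0.227, with a 95% interval from -0.43 to 0.00, so the same holds.

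**Step 3: how often this happens.** The lower 95% limit lies above -0.33 only if the observed r is weaker than -tanh(0.3428 - 0.2310) = -0.111. In SE units this is -(2.909 - 1.960) = -0.949. With m = -atanh(|true r|)/SE, the share of one-sided non-significant results whose 95% interval contains -0.33 is

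[Phi(-0.949 - m) - Phi(-1.645 - m)] / [1 - Phi(-1.645 - m)].

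| True r | Non-significant, one-sided | Of these, 95% interval contains -0.33 | Of these, one-sided 95% bound does not exclude -0.33 |
|---|---|---|---|
| 0 | 95% | 13% | 6% |
| -0.10 | 79% | 31% | 16% |
| -0.20 | 47% | 53% | 31% |

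**Step 4: when the true correlation is -0.33.** A site is non-significant with probability 1 - 0.897 = 10.3%, or 17% at the stated power. Over five independent sites, the chance of at least one non-significant result is 1 - 0.897^5 = 42%, or 61% at about 83% power.

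**Step 5: the positive side.** If the true r is +0.33, the one-sided test for a negative correlation is non-significant in practically every sample. Non-significance carries no information against +0.33.

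**Step 6: what 75 subjects can exclude when r = 0, using confidence limits.**
- Excluding -0.33 by the 95% interval: Phi(0.949) = 82.9%.
- Excluding -0.33 by a one-sided 95% bound: Phi(1.264) = 89.7%.
- Excluding both -0.33 and +0.33 by the 95% interval: 2 x 0.829 - 1 = 65.7%. With a 90% interval it is 79.4%.

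**The case against.** Several points can be made for the plan, and most of them stand.

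- **Nothing depends on the sentence.** It introduces the between-population calculation, whose power figures come from an assumed correlation of 0.85 with 5, 7 or 10 observations. No rule says that a non-significant site excludes anything. This stands: over-reading is a risk, not a planned step.
- **The sample nearly has the claimed property.** In the hypothesised direction, and judged by a confidence limit, 75 subjects exclude -0.33 with 83% to 90% probability when r = 0. This stands. It is a property of the interval when the true correlation is zero, however, and not of the test result that item 3 relies on.
- **The absolute-value wording may be shorthand.** Item 1 uses similar wording to mean a stronger negative correlation. That is a fair reading, but item 3 as written covers both signs.
- **Safeguards exist.** The intervals are planned, and D.8 concedes a false-negative risk. The concession arises mainly from the group contrasts, and the intervals are not tied to claims of absence.
- **The null statements are general.** B.9 and D.8 concern the overall activity-obesity hypothesis, not a single DLW site, and accelerometry covers all 500 participants per site. This limits the consequence.

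A reader might set 66% against the stated 83% and infer that the sample falls short. That comparison is not like for like: 66% is for excluding both signs when r = 0, while 83% is for detecting one sign when r = -0.33. A reader might also infer that many null sites would be read wrongly. At true values of -0.10 or -0.20, the statement that the correlation is weaker than 0.33 is true, so the inference would be under-supported, not false.

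**Conclusion.** The exclusion claim in D.7.2 item 3 does not follow from item 1 and should be corrected. A non-significant site result can leave -0.33 inside its 95% interval, in about 13% to 53% of such results for true correlations from 0 to -0.20, and it says nothing about +0.33. The consequence is confined to interpretation: a null DLW site could be over-read. The documents do not show that it would be, and the sample size, planned tests and between-population power figures are unaffected.

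The figures assume the Fisher-z approximation, 75 evaluable DLW subjects per site and, in the five-site figure, independent sites. The true correlations of 0, -0.10 and -0.20 are illustrative.

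The documents do not support treating 0.33 as an equivalence margin. They give it as a detectable correlation for DLW at 75 per site, so no fixed ±0.33 rule need be imposed, and it should not be carried over to the accelerometer data.

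**What to change.** 1. In D.7.2 item 3, replace the exclusion claim with a statement that the within-site DLW samples can *detect a negative correlation of -0.33 with the stated power*.
2. State, in D.7.1.1.1 or D.8, that any claim of absence will rest on the confidence intervals already planned in D.7.1.1.1 and not on non-significance.
3. If an exclusion statement is kept, give its probability at 75 subjects when r = 0: about 83% for excluding -0.33 by the 95% interval, and about 66% for excluding both -0.33 and +0.33.
4. While editing, reconcile the 83% in item 1 with its inputs: say whether the test is two-sided or whether about 60 evaluable subjects were assumed.

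The cost is a few sentences. No data, sample size, test or estimate changes. The stated property of the DLW sample becomes narrower, and what a null site result can support becomes clear before the data are seen.
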